Adolescent anorexia nervosa is a severe eating disorder related to long-lasting morbidity and premature mortality (1, 2), and recent reports from hospitals suggests the prevalence in Norway may be increasing (3). The manualised family therapy “Family Based Treatment” (FBT) is currently the treatment approach for adolescent anorexia nervosa with the largest evidence base (4). FBT is recommended as a first line treatment in multiple service contexts (5, 6).

While there has been conducted several randomised controlled trials of FBT in academic settings (7), there are few large studies examining outcomes when FBT is implemented in clinical practice. A

systematic review published in 2015 found five such dissemination studies. Of these, three were conducted in academic clinical settings with the number of patients ranging from 11 to 20, and two were retrospective studies reporting changes in service use patterns after implementation of FBT in a regular mental health service (8). Two later studies have compared the outcomes achieved in clinical trials of FBT to those of FBT provided in regular clinical care, finding these to be comparable (9, 10), but these have both been conducted in highly specialised clinical contexts. More studies with higher power are needed to confirm the effectiveness of FBT when disseminated to regular healthcare contexts.

At the Child and Adolescent Mental Health Service (CAMHS) unit Nedre Romerike BUP, adolescent anorexia nervosa has consistently been treated with family therapy for about 20 years. In 2018 the unit implemented FBT, making several changes to the form of family therapy provided. As part of treatment monitoring, patients are weighed regularly, and weight data are recorded in patient health records.

Restrictive eating and corresponding weight loss are core features of anorexia nervosa, besides distorted views of the body and rigid preoccupation with losing weight and avoiding weight gain. Normalisation of eating behaviour and weight status is hence the primary treatment goal, making the patient health records in this case contain relevant outcome data.

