The long-term course of anorexia nervosa is heterogeneous, and in some patients the disorder shows a protracted course, with long term morbidity and functional impairment, as well as increased mortality (11). There are few longitudinal studies of treatment outcomes with long follow-up periods (12). As Norway has a general system of personal identification numbers, following up patients across multiple public registries is a viable way to assess long term outcomes without the patients needing to participate in reporting.

AIMS

The primary aim is to assess the short and long-term effectiveness of FBT compared with non-manualised family therapy. This is operationalised as testing whether the adoption of FBT has led to patients achieving normalisation of weight faster than with the previously delivered family therapy, and whether it will lead to less treatment provided for eating disorders in adulthood. Secondary aims are to assess whether adoption of FBT have resulted in reduced time to discharge, changed the heterogeneity of weight gain across patients, whether there have been changes in the rates of adverse events and readmissions, and to assess whether the implementation of FBT has led to changes in long-term functional status and rate of mortality.

DESIGN AND METHODS

Participants and recruitment

This is a two-group retrospective exploratory cohort study with prospective longitudinal follow-up in public registries. Eligible participants are all patients initiating treatment during the years 2015-2020 with the eating disorder team at Nedre Romerike BUP with a primary ICD-10 diagnosis of F50.0 Anorexia nervosa or F50.1 Atypical anorexia nervosa. Patients will be excluded if they were treated during the years 2018-2020 and FBT was never initiated. It is estimated that the final sample size will be approximately 200.

Eligible participants will be identified through review of patient health records. Participants will be contacted by letter with information about the study, including a link to an online video explaining more about the study. Study personnel will make a follow-up telephone call approximately a week later to allow the eligible participant to ask any questions they may have before deciding on participation in the study. Participants who are interested in participating will be directed to a website

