where they can sign an electronic consent form and complete a short survey about their experience of treatment. The consent form and treatment experience survey will be implemented in “Tjenester for Sensitive Data”, which has appropriate security and allows for verified electronic signatures.

Participants will be contacted after they have reached age 16, and thus are able to give informed consent. They will be encouraged to discuss participation with their parents or other legal guardians.

Endpoints and data collection

Primary endpoint for the retrospective study is weight restoration, defined by patients having a weight measurement placing them at or above 95% of expected body weight (50. percentile) for age given Norwegian population norms, following established definitions of weight restoration (10).

Secondary endpoints are discharge from treatment and readmission to treatment (the latter is assumed to be right-censored).

Adverse events will be defined as debut of suicidal ideation, attempted suicide, debut of self-harming behaviour, severe self-harm where medical attention is indicated, hospitalisation for low weight or medical complications from low weight, admission to inpatient treatment for anorexia nervosa, involuntary gastric tube feeding, parental separation, and initiation of contact with child protective services.

Participant experiences and satisfaction with services will be assessed using the Generic Short Patient Experiences Questionnaire (GS-PEQ) (13).

The primary endpoint for the prospective study is continued morbidity, defined as being currently in treatment in specialist health care for any eating disorder. Secondary endpoints are mortality, level of education and employment status.

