Data for the retrospective part of the study will be extracted from electronic patient health records. Weight data will be extracted directly from the electronic patient health record system (DIPS). One researcher will further go manually through all records of included patients and extract dates of treatment start, adverse events, discharge and any readmission, as well as checking the record for any weight measurements recorded but not entered into the weight database. As covariates we will also extract age, sex, gender, family structure, extent of care benefits received during treatment (pleiepenging), and comorbid disorders (ICD-10 diagnoses). Another researcher will independently extract data from a random 10% subsample for control and reliability assessment of coding.

Each participant will be assigned a random case identity number, which will be used for identification in all dataset files when data is analysed. Participant national identity numbers will be stored along with the corresponding case identity number in a separate file, the identity key file. Access to the identity key file will be restricted to the project manager and researchers performing data extraction. It will also be delivered to the agencies maintaining the relevant public registries.

When extracted, data will be entered directly into a REDCap database maintained by Akershus university hospital. Access will be restricted to researchers in the project group. Data will be stored and analysed de-identified.

Data for the prospective part of the study will be acquired from the following public registries: Norwegian Patient Registry, Norwegian Cause of Death Registry, and the databases “Attachment to employment, education and welfare benefits” and “Educational attainment of the population” collated by Statistics Norway. Data will be acquired from these databases in three waves; five, ten and twenty years after the last participant initiated treatment. All registry data will be acquired, stored and analysed de-identified.

Analysis plan

Statistical analysis will be conducted in a Bayesian framework using the Stan platform through the R (14) package brms (15).

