We will evaluate whether adoption of FBT has led to faster weight normalisation by fitting a parametric survival model to the number of days until weight restoration is achieved. We will also fit models with gender, age, baseline weight, comorbid disorders and family structure as covariates, and further investigate whether any of these act as moderators of FBT compared with previous treatment. Similar parametric survival models will also be used for modelling differences in time to discharge and readmission. Differences in the rate of adverse events will be modelled using Poisson regression.

We will also evaluate differences between the cohorts in treatment course by fitting multilevel spline models to weight data with knots for every 4 weeks in treatment. Weight measurements will be nested within patients, and patients nested within cohorts. Spline models will allow for modelling non-linear weight change over the course of treatment, and the multilevel structure at the patient level will allow us to evaluate changes in heterogeneity of treatment response pre and post adoption of FBT, as well as visualise trends and heterogeneity of weight change across the course of treatment.

Analysis of prospective data will use parametric survival models or logistic or ordinal regression models, depending on the level of time specificity available in the data.

We have conducted simulations to investigate statistical power, assessing the type S (sign) and type M (magnitude) error rates, given inference based on the posterior median. We made the assumption of achieving at least a sample size of 150 patients and that implementation of FBT has led to a 10% increase in the probability of an event (i. e. weight restoration or discharge). With 1000 simulations, we estimated a type S error of 0.00 and an M error of 0.89, suggesting a very low risk of estimating the sign of the effect incorrectly and a small risk of underestimating the effect size. We conclude that the study will be adequately powered to achieve its primary aim.

The analysis will employ weakly informative prior distributions, using previous studies and other external knowledge (for instance about the biological limits of weight gain per day) to construct priors that rule out impossible areas of the parameter space (17).

ETHICAL CONSIDERATIONS

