This study does not involve any direct experimental manipulation, and as long as the process of extracting and analysing data from patient health records and public registries is conducted with due care, there is no risk of harm to the participants. FBT has been widely implemented in Norwegian health care based on findings from experimental studies in treatment settings quite different from regular public healthcare services. Research on the short and long-term effectiveness of FBT in a Norwegian context hence has considerable value to society and future patients receiving treatment for anorexia nervosa.

STUDY TIMELINE AND PLANS FOR DISSEMINATION

The study was approved with qualifications by the Regional Ethics Committee in 2021 with a requirement to adjust the protocol to seek informed consent from all participants or their legal guardians. Final approval was granted in July 2022. The process of identifying and contacting eligible participants will start as soon as approval is received.

Data extraction for the retrospective part of the study will start for each participant as soon as informed consent is obtained. It is expected to be finished at the latest in the fourth quarter of 2023, with reliability checking completed within 2023. Preparation of computer code for analysis will be done concurrently, and analysis will commence when data extraction is completed. Preparation of reports

for publication will be done during 2023 and early 2024. Findings will be submitted to international scientific journals specialising in eating disorders. Abbreviated reports of findings will also be prepared and submitted to the journals of relevant Norwegian professional associations.

For the prospective part of the study data will be extracted in four waves, when the participant last initiating treatment has reached the planned time for follow-up and registries are updated. An individual follow-up date will be calculated for each participant, to adjust for differences in when participants initiated treatment, and the closest relevant registry entry to that date will be extracted. The project group will consult with the agencies maintaining the registries to plan data extraction in detail. Findings from the prospective part of the study will be reported in international scientific journals as they become available.

DATA RETENTION

Documentation for the clinical study will be retained for five years after final study report/publication.

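### Adverse events have no common observation window or stated exposure, although the earlier cohort has about three more years of potential record

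*Combined protocol and SAP*

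**What the plan says.** Endpoints and data collection lists nine types of adverse event, beginning: "Adverse events will be defined as debut of suicidal ideation, attempted suicide, debut of self-harming behaviour". No period is attached to any of them. Two of the nine are first-occurrence (debut) events.

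The same section describes collection: "One researcher will further go manually through all records of included patients and extract dates of treatment start, adverse events, discharge and any readmission". It does not say how far back or forward the search runs, or whether events before treatment start or after discharge count. The Analysis plan adds only: "Differences in the rate of adverse events will be modelled using Poisson regression". It mentions neither an offset nor person-time.

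The calendar comes from three other places. Participants and recruitment: "Eligible participants are all patients initiating treatment during the years 2015-2020 with the eating disorder team". Background: "In 2018 the unit implemented FBT". Study timeline: "Final approval was granted in July 2022", after which extraction starts patient by patient on consent and ends by the fourth quarter of 2023. No common cut-off date is given.

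On treatment length, Aims says: "Secondary aims are to assess whether adoption of FBT have resulted in reduced time to discharge".

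Unequal follow-up is dealt with elsewhere. Readmission is taken as right-censored, and registry follow-up uses an individual date for each participant. Neither device is applied to adverse events.

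**The concern.** A count of events per patient depends on how long each patient is observed. Here the potential observation time after treatment start differs between the cohorts by construction, because they started in different calendar years and are extracted over the same later period. Time in treatment may differ as well, since that is one of the study's own questions.

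The usual remedy, dividing by person-time, works only if the event rate is constant over follow-up. Some listed events, such as hospitalisation for low weight or inpatient admission, could plausibly cluster early. If they do, the cohort with less follow-up keeps mainly its high-risk early time, and its rate rises.

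At stake is the direction of a safety comparison. The same patients, at the same true risk, could appear to have fewer or more adverse events with FBT depending on a choice that the plan leaves open, in a retrospective study where that choice could be made after the data are seen.

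**Working it through.** The documents give no event count, rate or power figure for adverse events, so there is no figure of the plan's to reproduce. (The type S and type M figures concern weight restoration or discharge.) Every event rate below is an assumption, and the true risk is always the same in both cohorts. Ratios are FBT over earlier cohort.

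**1. Potential record length.** With uniform starts within each three-year block, the cohort midpoints are mid-2016 and mid-2019.

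| Extraction | Earlier cohort, years | FBT cohort, years | Ratio |
|---|---|---|---|
| July 2022 | 6.0 (4.5-7.5) | 3.0 (1.5-4.5) | 0.50 |
| Start of Q4 2023 | 7.25 | 4.25 | 0.59 |
| End of 2023 | 7.5 (6-9) | 4.5 (3-6) | 0.60 |

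The difference is three years throughout.

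**2. Whole record, early clustering.** Assume 1.0 event/year for the first 3 months, 0.3/year for the rest of the first year, then *h* per year. First-year events: 0.25 × 1.0 + 0.75 × 0.3 = 0.475. With 7.25 v 4.25 years:

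- Counts, no offset: (0.475 + 3.25*h*) / (0.475 + 6.25*h*)
- Rates, with offset: the count ratio × 7.25/4.25 = the count ratio × 1.706

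| *h* | No offset | With offset |
|---|---|---|
| 0.05 | 0.6375/0.7875 = 0.81 | 1.38 |
| 0.1 | 0.800/1.100 = 0.73 | 1.24 |
| 0.3 | 1.450/2.350 = 0.62 | 1.05 |

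**3. Simulation with other rates.** 1,500 runs per scenario, 75 or 100 patients per cohort (equal halves of 150 and about 200; the split is not stated), extraction in July 2022 or at end 2023. A two-sided 5% Wald test on the log rate ratio stands in for a 95% posterior interval.

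| Scenario | Ratio | Falsely excludes 1 |
|---|---|---|
| Constant 0.2-0.4/year, no offset | 0.50-0.60 | 92-100% |
| Constant 0.2-0.4/year, offset | 0.99-1.00 | 4-7% |
| 0.6 in year 1, then 0.1-0.2, no offset | 0.62-0.76 | 41-96% |
| 0.6 in year 1, then 0.1-0.2, offset | 1.14-1.45 | 19-71% |

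If records end at age 18 (start age assumed to be 12 to 17.5), the no-offset ratios in this set move to 0.73-0.97.

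**4. Treatment period only.** Read the power section's 10% increase in event probability as mean treatment of 1.0 v 1/1.1 = 0.91 years. With the rates of step 2, events are 0.475 v 0.25 + 0.3 × 0.659 = 0.448. The count ratio is 0.94, and the rate ratio is (0.448/0.909)/0.475 = 1.04. With a constant rate these would be 0.91 and 1.00. For a larger assumed difference, 12 v 9 months, events are 0.475 v 0.400: 0.84 on counts, and 0.533/0.475 = 1.12 on rates.

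**5. Common window.** With 12 months from treatment start in both cohorts, the expected ratio is 0.475/0.475 = 1.00. The simulation of step 3 gives 0.99-1.01, with 3-5% false exclusions. The shortest potential follow-up, from end 2020 to July 2022, is 1.5 years, so 12 months is feasible in calendar terms for every patient. This result assumes that events after discharge are recorded. If they are not, and treatment lasts 12 v 9 months, the window gives 0.400/0.475 = 0.84 when 12 months are credited as observed, or 1.12 when observation ends at discharge. Comparing the first 9 months only gives 0.400/0.400 = 1.00.

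**The case against.** The strongest reply is that the plan is brief rather than wrong. It speaks of a rate, and a Poisson model of a rate normally carries a person-time offset; the dates needed to build one are collected. A reader might infer that the plan fits the model without an exposure term, but the documents do not say so. What stands against the reply is that an offset alone is enough only under a constant hazard (step 3).

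A reader might also infer that treatment length differs between the cohorts. The documents do not support this as fact: shorter time to discharge is a secondary aim and a power-simulation assumption. The 0.84 and 1.12 pair rests on 12 v 9 months, which has no source in the plan; the 10% reading gives 0.94 and 1.04. The calendar imbalance does not depend on this.

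Nor do the documents say that each patient's whole record to extraction will be searched. The wording can mean the record of every included patient, and in a child and adolescent service records may close at discharge or at 18. That shrinks the distortion without reliably removing it. Debut events cannot accumulate over years as a constant-rate count does, and early clustering is itself an assumption.

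Finally, on-treatment events are a legitimate target, and readmission already captures part of what happens after discharge. A window running past discharge is therefore not the only defensible choice, and it is fair only as far as later events are recorded.

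**Conclusion.** The point holds as an omission with consequences: adverse events have no common window, end of observation or stated exposure, while potential record length differs by about three years between cohorts. At equal risk and under the assumed rates, whole-record counts without an offset favour FBT (about 0.6-0.8 in step 2, as low as 0.50 with a constant rate, and 0.73-0.97 for the step 3 rates if records end at 18). Whole-record rates with an offset are unbiased under a constant hazard and favour the earlier cohort under early clustering (about 1.05-1.4). A treatment-period comparison shifts by about 4-6% under early clustering with a 10% shortening, and by more with a larger difference.

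The existence of the gap and the calendar imbalance are firm. The size of any distortion is conditional on event rates and record closure, for which the documents give no figures. It would go too far to say that the adverse-event result will be biased, or in which direction. This is a secondary aim of an exploratory study, and the primary endpoint is untouched. The change is worth making before analysis because it is cheap.

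**What to change.** In Endpoints and data collection and in the Analysis plan:

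- Count only events dated after treatment start, within one fixed window that is the same for both cohorts (for example 12 months).
- Use log observed time in the window as an offset, with observation ending when the record can no longer capture events.
- Analyse debut events as time to first event among patients without a prior history.
- Report events before and after discharge separately, and add an on-treatment sensitivity analysis over the same early period in both cohorts.

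The cost is a few sentences. Dates of treatment start, events and discharge are already to be extracted; prior history of the debut events and the end of usable record would need to be coded too.

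Two downsides should be stated. Events after the window leave the main comparison. Events after discharge may be under-recorded for patients whom the unit no longer sees, so the post-discharge comparison should rest mainly on events captured regardless of attendance, such as hospital admissions, and be interpreted with caution.

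### The scale of the spline outcome and of baseline weight is not defined; read as recorded weight, they do not match the age-referenced primary endpoint

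*Combined protocol and SAP*

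**What the plan says.** Endpoints and data collection defines weight restoration on an age-referenced scale: a weight "at or above 95% of expected body weight (50. percentile) for age given Norwegian population norms".

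The Analysis plan then uses weight in two further places without naming a scale:

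- Treatment course and its heterogeneity are studied by "fitting multilevel spline models to weight data with knots for every 4 weeks in treatment", with weighings nested in patients and patients in cohorts. No age or sex term is named for this model.
- The adjusted survival models take "gender, age, baseline weight, comorbid disorders and family structure as covariates", and the investigators will "further investigate whether any of these act as moderators of FBT compared with previous treatment".

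Elsewhere the term refers to recorded weighings. Background says that "patients are weighed regularly, and weight data are recorded in patient health records", and Endpoints and data collection describes taking weight data straight from the record system. The example given for the priors is external knowledge, "for instance about the biological limits of weight gain per day". Aims lists a change in the heterogeneity of weight gain as a secondary aim.

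**The concern.** Adolescents grow, so a kilogram does not represent the same degree of recovery at 12 as at 16, and the restoration threshold rises with age. If the splines are fitted to kilograms, three things follow:

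- A cohort's curve can rise while its patients stand still on the scale that defines the primary endpoint.
- The patient-level spread of weight level mixes body size and age with severity.
- The same baseline kilograms lie at different distances from the 95% line at different ages, so an interaction between baseline weight and treatment may partly reflect age.

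At stake are the interpretation of the weight curves and of one moderator analysis. The primary outcome is already age-referenced and is not touched.

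**Working it through.** The plan states no figure for the weight-course model. Its simulation (type S 0.00, type M 0.89) concerns event endpoints and does not bear on this point. The documents give no norms and no age distribution, so every weight and age below is an assumption.

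**1. Single-patient illustration.** Assumed expected weights: 43 kg at 12, 48 at 13, 52 at 14, 55 at 15, 57 at 16, 58.5 at 17.

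- Gain in one year at a constant 85% of expected = 0.85 × (expected weight one year later − expected weight now): 0.85 × 5 = 4.25 kg from age 12; 0.85 × 3 = 2.55 kg from 14; 0.85 × 1.5 = 1.28 kg from 16. None of these is recovery.
- Constant kilograms from 90% at age 12: 0.90 × 43 / 48 = 80.6% a year later.
- A baseline of 42 kg is 42/43 = 98% of expected at 12 and 42/57 = 74% at 16.

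**2. Growth within a cohort's curve.** A second assumed curve is E(a) = 42 + g(a − 12) + [(0.5 − g)/12](a − 12)², with growth g of 3 or 5 kg/year at age 12, slowing to 0.5 kg/year at 18. Patients start at 80% of expected (SD 6 points) and gain 13 points in a year (SD 6). Mean age is 15 (SD 1.3, limited to 12–17). For a patient at these means:

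- g = 3: E(15) = 49.13, E(16) = 50.67. Growth at constant percent = 0.80 × 1.54 = 1.23 kg. Total gain = 0.93 × 50.67 − 0.80 × 49.13 = 7.82 kg. Share 16%.
- g = 5: E(15) = 53.63, E(16) = 56.00. Growth = 0.80 × 2.375 = 1.90 kg. Total gain = 0.93 × 56.00 − 0.80 × 53.63 = 9.18 kg. Share 21%.

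Simulation of 200,000 patients per cohort agrees: 1.24 of 7.79 kg and 1.92 of 9.11 kg.

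**3. False difference between cohorts.** Both cohorts have the same course in percent of expected weight, so the true difference is zero. In kilograms, the simulated difference in one-year gain is:

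- equal ages: 0.0 kg
- one cohort 0.5 year younger: 0.07 to 0.15 kg
- one cohort 1 year younger: 0.13 to 0.29 kg

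The between-patient SD of gain is 3.0 to 3.4 kg, so the largest value is about 0.09 SD (0.29/3.37). By hand for g = 5 and mean age 14: 0.93 × 53.63 − 0.80 × 50.50 = 9.47 kg, which is 0.29 above 9.18. A further check with age SDs of 1.0 to 1.6 years gave about 0.15 to 0.4 kg for gaps of 0.5 to 1 year.

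**4. Heterogeneity.** Age explains 27 to 44% of the variance of baseline kilograms but only 0.4 to 1.4% of the variance of gain. Widening the age SD from 1.3 to 1.8 moves the SD of baseline weight from 3.44 to 3.72 kg (g = 3) and from 4.27 to 4.86 kg (g = 5). The SD of gain hardly changes (3.03 to 3.02 and 3.37 to 3.33 kg).

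**5. Baseline weight.** Baseline kilograms correlate 0.75 to 0.85 with baseline percent of expected weight; after adjustment for age, 0.985 to 0.994.

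**The case against.** The strongest objection is that the plan nowhere says kilograms. The prior example is only an example and applies to the analysis in general, so the defect is silence about a scale, not a demonstrated wrong choice. That stands. Recorded weight is the plain reading, but it is inferred.

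A reader might go further and infer that growth will be counted as an effect of FBT and that age differences will appear as changed heterogeneity. The documents do not support this. The planned comparison is between cohorts, and growth common to both cancels. Bias needs the cohorts to differ in age, sex or length of treatment, and no such difference is reported. The aim concerns heterogeneity of gain, where step 4 shows age matters very little.

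There is one reason to expect some age difference. Participants and recruitment has patients contacted only from age 16, and the timeline ends extraction in the fourth quarter of 2023. On those dates, someone starting in 2020 must have been at least about 12 to 13 at the start (16 minus three to four years). For 2015–2017 starters the floor is about 7 to 10 and hardly binds. The rule could therefore trim the youngest patients from the FBT cohort only. In step 3 the older cohort gains slightly less in kilograms, so this would work slightly against FBT. Its size is unknown.

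A reader might also infer that baseline weight is a faulty covariate. As a main effect it is not: age and gender stand beside it, and with age adjusted the two scales carry nearly the same information. The moderator point survives, because the plan does not say whether an age-by-treatment term accompanies the baseline-weight interaction.

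Finally, percent of expected weight is not neutral either. On the weights in step 1, a gain of 6.45 kg is 15 points at age 12 (6.45/43) but 11.3 points at 16 (6.45/57). The zero difference on that scale in step 3 holds by construction. What favours it is agreement with the study's own definition of recovery.

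**Conclusion.** The point holds in a limited form. The scale of the spline outcome and of baseline weight is undefined, and its plain reading does not match the primary endpoint. On a kilogram scale, about one-fifth of a cohort's one-year gain would be growth, the spread of weight level would include body size and age, and a baseline-weight moderator without an age interaction would be partly an age moderator. Bias in the cohort difference and in the heterogeneity of gain is small unless the cohorts differ clearly in age or sex.

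These sizes rest on assumed norms and an assumed age distribution. The simulation used one weight-for-age curve for all patients, so the effect of sex mix was not tested. This is a worthwhile, inexpensive improvement to a secondary analysis and does not threaten the primary result.

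**What to change.** Add one or two sentences to the Analysis plan:

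- State that the multilevel spline models are fitted to percent of expected body weight for age, using the same norms as the primary endpoint.
- Enter baseline percent of expected weight, in place of baseline weight, as covariate and moderator in the survival models.
- Rescale the prior on weight gain to that scale.
- Keep kilogram curves as a descriptive supplement.

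No new data are needed, since each weighing must already be placed against the norm to determine restoration. The costs are curves that are less directly readable and a prior that must be re-expressed. One limit remains: weight for age does not account for height, which is not among the listed covariates, so stature would still be mixed with recovery.
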